15.4.3 Secondary Safety Endpoints

The safety secondary objective for part B is to evaluate the long term safety profile of the GBS-NN vaccine up to 1 year following the first dose.

The same endpoints will be evaluated as for the primary objective.

15.4.4 Secondary Immunological Endpoints

The secondary immunological objectives for both parts of the study are:

- To evaluate IgG antibody responses induced by different vaccine doses alone or in the presence of Alhydrogel over time in healthy female volunteers:
- To determine the impact of pre-existing antibody levels on the vaccine-induced antibody response:

In addition for Part A:

- To determine the effect of Alhydrogel® adjuvant on the immunogenicity of GBS-NN vaccine
- To select the dose levels and regimens for vaccination of cohorts in Part B, based on the antibody levels at 8 weeks following the first dose (Day 57)

In addition for Part B:

- To evaluate the immune response to the GBS-NN vaccine up to 1 year following the first dose

Immunological parameters measured to evaluate objectives

In order to evaluate these objectives, GBS-NN specific IgG concentrations will be determined by ELISA against a reference standard human antibody preparation of known concentration as described in the laboratory protocol and used to derive the following parameters for each volunteer:

- Antibody concentration at each sample point ($\mu\text{g/mL}$)
- Fold increase over pre-immunisation level (Day 1) in antibody concentration at each sample point (ratio)

Specific Endpoints calculated from immunological parameters

These parameters will be used to derive the following endpoints at all time-points according to the treatment group:

- Geometric mean antibody concentration (with 95% c.i.)
- Geometric mean fold increase in antibody concentration (with 95% c.i.)
- Seroconversion rate at each sample point (proportion of volunteers with fold increase above threshold (*see below))
- At the primary immunological endpoint (Day 85) all groups in Part A will be analysed according to the proportion of volunteers whose specific antibody level ($\mu\text{g/mL}$) exceeds the following thresholds: 0.5; 1.0; 2.0; 4.0; 8.0 $\mu\text{g/mL}$. The analysis will be repeated for Part B, where the threshold values may be adjusted based on the results of Part A.

* For Part A the threshold to define a positive response will be set arbitrarily to 2.5-fold rise above base-line, as is common practice in FIM vaccine studies. For Part B, the threshold will be set based upon the data derived from Part A. The fold increase for all 12 placebo recipients at Days 29, 43, 57 & 85 will be considered. The mean and standard deviation will be calculated and the cut-off defined as two standard deviations above the mean.

The primary immunological endpoints (still secondary study endpoint) for both Part A and Part B will be the values of these endpoints at Day 85, 12 weeks after the administration of the first dose of vaccine).

In Part A, the immunological endpoints at Days 1, 29 and 57 will be reported separately by group in a blinded fashion to enable the dose selection for Part B

Additional analyses to address objectives

For each group the individual data will be presented as scatter plots and cumulative frequency distributions at each time-point

Correlation plots will be generated to compare the specific antibody concentrations before vaccination and at 12 weeks after the first dose to evaluate the influence of pre-existing antibody levels on responses.

Statistical significance of differences in endpoint values

Statistical tests will be carried out to compare results between treatment groups, depending on studied variable type (see section inferential statistics). These analyses will be fully detailed in the SAP. In brief the following comparisons between groups will be made at Day 29 and Day 84 (and at Day 57 in Part A only):

Part A:

- Placebo group (total 12 volunteers, 6 with buffer only and 6 with alhydrogel) against all other dose groups
- Each dose level with and without Alhydrogel®
- 10µg vs 50µg, 10µg vs 250µg, 50µg vs 250µg in volunteers vaccinated with GBS-NN alone
- 10µg vs 50µg, 10µg vs 250µg, 50µg vs 250µg in volunteers vaccinated with GBS-NN in the presence of Alhydrogel
- For all groups and parameters Day 29 vs Day 85

Part B:

- Placebo group against all other dose groups (regimens to be decided)
- Group A vs Group B; Group A vs Group C; Group B vs GroupC
- For all groups and parameters Day 29 vs Day 85

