6.2 Rationale for Study

A large medical need exist for the development of an effective alternative to IAP for the prevention of neonatal GBS infections, as outlined above.

Maternal immunization of pregnant women during the latter part of pregnancy leading to passive immunization of the unborn child through trans-placental transfer of protective GBS-specific antibodies would be beneficial. Such antibodies will likely persist for 3-6 months after birth and likely protect both the foetus in-utero against GBS induced still birth and premature delivery; and the newborn baby against both EOD and LOD. A vaccine therefore seems the obvious choice for an alternative to IAP.

A number of GBS serotypes can be distinguished based on their type-specific capsular polysaccharides (CPS). This capsule represents a major virulence factor, which helps bacterial invasion by interfering with phagocytic clearance except in the presence of type specific opsonophagocytic antibodies (Baker 2000, Nizer et al., 2000). To date, 10 antigenically unique GBS serotypes have been identified (Ia, Ib, II-IX). Of these serotypes Ia, III and V are the most prevalent in EOD with type III accounting for 36% of EOD and 71 % of LOD, and together, serotypes Ia, Ib, II, III and V cover approximately 95% of all isolates.

Spontaneous colonization of women with GBS is the likely explanation for the existence of naturally occurring antibodies against several GBS antigens in pregnant women. Interestingly, the presence of high levels of anti-CPS antibodies in pregnant women has been found to correlate with protection of their off-spring against invasive GBS disease, indicating that vaccine-induced maternal anti-CPS antibodies would indeed be protective (Baker and Kasper, 1976; Lin et al., 2001; Lin et al., 2004). Indeed, CPS-based vaccines

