6.3 Risk/Benefit Assessment

Antibodies against both full-length Rib and Alpha proteins, [REDACTED] as well as antibodies reactive with the GBS-NN vaccine candidate, naturally occur in women exposed to GBS, and such antibodies are efficiently transferred to the unborn child *in-utero*. Many adults and new-born infants have, therefore, already been naturally exposed to both the proteins from which the antigen is derived and to antibodies against these proteins, and no side effects have been attributed as a consequence of such exposure in humans.

The planned excipients in the vaccine formulation are also all well-known from other vaccines, and no novel or non-tested components are used. The vaccine is adsorbed with a known adjuvant, Alhydrogel, (0.5 mg of Al³⁺ per dose), corresponding to the dose used in many other commercial vaccines. Volunteers will receive maximum of 2 dosing occasions in the clinic. The initial Phase I trial will include up to 310 healthy adult women using contraceptives – Part A enrolling up to 70 women and Part B enrolling up to 240 women. The vaccine will be given by the intramuscular route as was done in the animal safety studies. The Phase I trial will evaluate ascending dose levels of GBS-NN with and without Alhydrogel®.

A number of preclinical studies have been conducted in rats, rabbits and mini pigs. [REDACTED]

Initial safety and immunogenicity evaluation of escalating dose levels will select an appropriate dose for further evaluation in the target population of pregnant women to investigate if immunisation of pregnant women with GBS-NN can result in detectable IgG antibodies in the neonate that might provide protection to the new-born infants. [REDACTED]

[REDACTED] Thus doses of 10µg, 50µg and 250µg to be used in the present study will remain within the safety margins, and no overdosage is expected.

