7.3 Secondary Immunological Objectives

The secondary immunological objectives for both parts of the study are:

- To evaluate IgG antibody responses induced by different vaccine doses alone or in the presence of Alhydrogel over time in healthy female volunteers.
- To determine the impact of pre-existing antibody levels on the vaccine-induced antibody response.

In addition for Part A:

- To determine the effect of Alhydrogel® adjuvant on the immunogenicity of GBS-NN vaccine.
- To select the dose levels and regimens for vaccination of cohorts in Part B, based on the antibody levels at 8 weeks following the first dose (Day 57).

In addition for Part B:

- To evaluate the immune response to the GBS-NN vaccine up to 1 year following the first dose.

The following endpoints will be evaluated by group and time-point to support these objectives:

- Geometric mean antibody concentration in µg/mL.
- Geometric mean fold increase in antibody concentration.
- Seroconversion rate (proportion of volunteers with fold increase above threshold).

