12.2 Treatment Period and Post-Study Period

12.2.1 Part A

Volunteers will receive one of up to 7 dosing regimens of GBS-NN or placebo on 1 or 2 occasions – a primary dose will be administered at Visit 2 and volunteers will remain in the study unit for at least 8 hours post-dose, and if a booster dose is required, this will be administered at Visit 6. There will be a time interval of 4 weeks between Visit 2 and Visit 6, although this time interval may change if the dosing regimen is changed. There will be 10 volunteers in each group, 8 randomised to active and 2 to placebo. All cohorts in Part A will incorporate sentinel dosing of 2 volunteers in each cohort for the primary dose only: 1 on active treatment and 1 on placebo. No further volunteers in that cohort will be dosed until at least 24 hours after dosing the second volunteer, provided that there are no serious or unexplained safety issues as determined by the Investigator.

The decision to proceed with administration of the primary dose in subsequent cohorts will be made as described in Section 12.5.

The following assessments will be carried out at these visits:

Visit 2

A urine pregnancy test, brief physical examination, urine drugs of abuse test and alcohol breath test will be performed to confirm eligibility. Eligible volunteers will be randomised to receive active or placebo on 1 or 2 occasions (all volunteers will receive a primary dose at Visit 2 and a booster dose of the same medication (active or placebo) will be administered at Visit 6 if required). The dose administered, the number of doses and the time interval between doses will be dependent on the data generated from the preceding cohort and will be decided by the Safety Review Committee. A pharmacodynamic blood sample will be taken to measure pre-existing antibody levels prior to dosing. The primary dose will be administered at Visit 2 and volunteers will remain in the study unit for at least 8 hours post-dose. Vital signs will be recorded pre-dose and at 2 and 6 hours post-dose. A brief medical examination (including an assessment of the injection site) will be performed prior to discharge to ensure the volunteer is fit for discharge.

Visit 3

Visit 3 will be performed 24 hours (\pm 2 hours) after administration of the primary dose and an assessment of the injection site will be performed, vital signs will be recorded and AEs and concomitant medications will be reviewed.

Visit 4

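### A Day 1 against Week 12 IgG plot cannot by itself show whether pre-existing antibody influences the vaccine response, because a positive correlation is expected even with no influence

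*Combined protocol and SAP*

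**What the plan says.** The objective, for both parts, is stated in section 7.3 and repeated in section 15.4.4: "To determine the impact of pre-existing antibody levels on the vaccine-induced antibody response".

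Under the additional analyses in section 15.4.4, the plan gives one analysis for it: "Correlation plots will be generated to compare the specific antibody concentrations before vaccination and at 12 weeks after the first dose". The stated purpose is "to evaluate the influence of pre-existing antibody levels on responses".

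Three other statements matter:

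- **Assay.** "GBS-NN specific IgG concentrations will be determined by ELISA against a reference standard human antibody preparation of known concentration" (section 15.4.4). No step is described that separates natural from vaccine-induced antibody.
- **Natural antibody.** Section 6.3 says that "antibodies reactive with the GBS-NN vaccine candidate, naturally occur in women exposed to GBS". Section 6.2 gives a cause for natural antibody to GBS antigens in general: "Spontaneous colonization of women with GBS is the likely explanation for the existence of naturally occurring antibodies".
- **Baseline.** The Day 1 sample is drawn before dosing ("A pharmacodynamic blood sample will be taken to measure pre-existing antibody levels prior to dosing", section 12.2.1; section 12.2.2 has the same for Part B). A rise relative to baseline is derived for each volunteer ("Fold increase over pre-immunisation level (Day 1) in antibody concentration at each sample point (ratio", section 15.4.4), but it is not related to the Day 1 level.

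The text gives no baseline term, baseline subgroup, reference value for no influence, or placebo comparator for this objective.

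**The concern.** The objective concerns the antibody the vaccine induces. The plotted outcome is total specific IgG at Week 12, which is persisting natural antibody plus induced antibody. Part of the vertical axis is therefore the horizontal axis again. A placebo recipient whose natural IgG is stable falls on the identity line with no vaccine response at all. A vaccine that gives every woman the same increment also produces an upward plot. So the plot cannot separate baseline helping the response from baseline merely persisting.

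The null correlation also falls as the response grows. Groups at different doses could show different correlations only because their responses differ in size.

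The question has practical weight. Sections 6.2 and 6.3 take the selected dose on to pregnant women, and section 6.2 says such women carry naturally occurring antibody. Whether that antibody boosts, blunts or leaves the response unchanged is what the objective is meant to tell the sponsor.

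**Working it through.** **Inputs.** From the plan: the plotted pair, the assay and the group sizes. Part A has 8 active and 2 placebo per cohort (section 12.2.1). Part B has up to 60 active and 20 placebo per cohort (section 12.2.2), so up to 3 × 20 = 60 placebo. The plan states no correlation, SD, response size or null value, so there is no figure to reproduce. All SDs and response sizes below are assumptions.

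**Step 1: constant added amount.** Let X be Day 1 IgG, r the fraction persisting to Week 12, and V the induced antibody, independent of X. Then Y = rX + V, and

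Cov(X, Y) = r·Var(X) > 0; corr = r·SD(X) / √(r²·Var(X) + Var(V)).

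Take r = 1, equal log-scale SDs, and V with geometric mean k times that of X. Then SD(V) = k·SD(X) and corr = 1/√(1 + k²):

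- k = 1: 1/√2 = 0.71
- k = 2: 1/√5 = 0.45
- k = 5: 1/√26 = 0.20
- k = 10: 1/√101 = 0.10

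**Step 2: constant fold rise.** Now log Y = log X + log F, with F independent of X, and corr = s_X / √(s_X² + s_F²). For natural-log SDs of 0.7 to 1.2 (baseline) and 0.5 to 1.5 (fold), the extremes are 0.7/√(0.49 + 2.25) = 0.42 and 1.2/√(1.44 + 0.25) = 0.92.

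The sign in both steps is algebraic and does not depend on the inputs. Only the size does.

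**Step 3: log-scale simulation with assay error.** The grid is Day 1 log10 SD 0.3, 0.5, 0.7; V at 2, 5, 10, 20 times baseline (geometric means); log10 SD of V, or of the fold rise, 0.3, 0.5; r = 1; assay error 0.1 log10 on each measurement; 400,000 draws per scenario. There is no influence of baseline in any row.

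| Quantity | Null | Result |
|---|---|---|
| Correlation, Day 1 v Week 12 | constant amount | 0.05 to 0.72 |
| Correlation, Day 1 v Week 12 | constant fold | 0.48 to 0.90 |
| Correlation, Day 1 v Week 12 | placebo | 0.90 to 0.98 |
| Correlation, fold rise v Day 1 | constant amount | −0.52 to −0.91 |
| Log-scale slope, vaccine minus placebo | constant amount | about −0.56 to −0.87 |
| Log-scale slope, vaccine minus placebo | constant fold | 0 |

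The second and third rows can be checked by hand. Placebo: 0.09/0.10 = 0.90 and 0.49/0.50 = 0.98. Constant fold: 0.09/√(0.10 × 0.35) = 0.48 and 0.49/√(0.50 × 0.59) = 0.90.

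The first row by response size is 0.30 to 0.72 at 2 times baseline, 0.16 to 0.54 at 5, 0.09 to 0.39 at 10, and 0.05 to 0.26 at 20.

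**Step 4: the obvious repairs.**

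- *Fold rise against Day 1* has Day 1 in its denominator, so under a constant amount it replaces a positive artefact with a negative one.
- *Log-scale slope difference* behaves the same way. Under a constant amount the vaccine slope is 0.06 to 0.39 against 0.90 to 0.98 for placebo. With Day 1 SD 0.5, a 5-fold increment and increment SD 0.3, the log model's vaccine-to-placebo ratio falls from about 21 at the 10th percentile of Day 1 to about 2.2 at the 90th, although the increment does not depend on baseline.
- *Week 12 minus Day 1* is distorted if natural antibody wanes. With r = 0.8 and natural-log SDs of 1.0, its null correlation with Day 1 is −0.18 when V equals baseline and −0.04 at 5 times.

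**Step 5: what placebo at the same Day 1 level supplies.** If natural antibody persists equally in both arms, E(Y | x, vaccine) − E(Y | x, placebo) = E(V | x). In µg/mL this is flat in x under a constant amount. The ratio of geometric means is flat in x under a constant fold. Each scale thus has its own clear null.

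**The case against.** **These are plots with no inference attached.** True as far as it goes: the plan gives no coefficient, test, threshold or decision rule. A reader might infer that a positive correlation will be reported as proof that baseline helps, but the documents do not say so. What stands against the objection is that the plan gives the plot the purpose of evaluating influence and supplies nothing to read it against. If a test were run on 60 volunteers (natural-log SDs of 1.0, constant amount), a significant positive correlation at two-sided 5% would appear in 97% of trials at 2 times baseline and 61% at 5 times, against 2.5% in that direction by chance. Since no test is planned, these figures only illustrate the risk.

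**The detail is left to the SAP.** Section 15 does say that the SAP will describe the planned analyses and that the protocol gives only some features. The text reviewed contains no separate SAP section on this objective, so a later repair cannot be ruled out. A reader should not infer that the sponsor has decided against one.

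**The artefact may be small.** This also stands in part. Under a constant amount it can be as low as 0.05 at 20 times baseline. The documents do not give the ratio, and under a constant fold the null correlation stays between 0.48 and 0.90 on the same grid.

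**The stakes are limited.** A reader might infer that Part B dose selection is affected. It is not: sections 7.3 and 10.1 base it on Day 57 IgG, with the safety profile.

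**Conclusion.** The point holds: the one analysis named for this secondary objective cannot answer it alone. That conclusion needs only that some natural antibody persists to Week 12 and that the ELISA does not separate it from induced antibody. The magnitude rests on the assumed SDs, response sizes and assay error, so the 0.05 to 0.72 range is conditional and is not a prediction for this trial.

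Two stronger conclusions are not supported. One is that a misleadingly strong correlation will certainly be seen: with a large response, or in a single Part A cohort of 8 active volunteers, it may not be. The other is that moving to fold rise or to a log-scale slope difference settles the matter. Both test only the constant-fold null and would suggest blunting if the vaccine simply adds the same amount at every baseline. It is a point the sponsor should correct, in a descriptive analysis of one secondary objective.

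**What to change.** In section 15.4.4 or the SAP, before the 12-week unblinding for Part B described in section 10.4:

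1. State what no influence means on each scale: a constant fold on the ratio scale, and a constant added µg/mL on the concentration scale.
2. Keep the plots, shown by group, with the placebo points and the identity line overlaid.
3. In Part B, with up to 60 placebo recipients as reference, estimate the vaccine-minus-placebo difference at low, median and high Day 1 IgG with 95% CIs, both as a ratio and in µg/mL. Use a model suited to each scale, each with a baseline-by-treatment term. Choose the Day 1 levels in advance and check for curvature in baseline, since log(X + V) is not linear in log X.
4. Do not report the log-scale slope difference as the sole answer.
5. State that neither a positive within-group concentration correlation nor a negative correlation of fold rise with Day 1 is by itself evidence of influence.

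The samples and assay results are already planned, so the cost is SAP wording and a small amount of extra analysis. The real burden is interpretive: the two scales may give different answers, and the report must present both.

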
Treatment Schedule for Part B:
	
Volunteers will provide written informed consent and will be screened for eligibility within 28 days before first study vaccine administration (Day 1). Eligible volunteers will receive one of 3 dosing regimens (X, Y or Z) of GBS-NN or placebo on 1 or 2 occasions – a primary dose will be administered on Day 1, and if a booster dose is required, this will be administered 4 weeks later. There will be up to 80 volunteers in each group, up to 60 randomised to active vaccine and up to 20 to placebo.
 
During the study, volunteers will attend study visits as described in the Schedule of Assessments, up to the post-study medical visit at Day 365. Safety assessments will be performed, vaginal and rectal swabs will be performed and pharmacodynamic blood samples will be collected at study visits according to the Schedule of Assessments.
 
[REDACTED]

Statistical Analysis:
	
Details of the planned analyses will be described in the SAP and some (but not all) important features are listed below and presented in the protocol statistical part:
 
Studied criteria for the two study parts

The following data (safety, immunogenicity and exploratory endpoints) will be described according to vaccine dose groups (and according to visits if relevant):

- Demographic and baseline data;
- Safety data including:
 - vital signs (heart rate, blood pressure, tympanic temperature and respiratory rate)
 - 12-lead ECG
 - safety laboratory tests (haematology, biochemistry)
 - urinalysis
 - adverse events
 - physical examinations
 - assessment results of the injection site (local reactogenicity) and systemic reactogenicity using scale variables;
- Pharmacodynamic blood sample results (antibody response).

Descriptive statistics

Descriptive statistics for quantitative parameters will be provided using number of observations (N), mean, standard deviation (SD), standard error of the mean (SEM), minimum, median and maximum. Descriptive statistics for qualitative parameters will be provided using absolute frequencies (n) and relative frequencies (%).

Inferential statistics

Statistical tests will be carried out to compare results between treatment groups, depending on studied variable type. These analyses will be fully detailed in the SAP.

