Given that GBS-NN has been found to be [REDACTED] protect against infections with serotypes Ia, Ib, II, III and V. And taken together with the finding that high levels of naturally occurring antibodies against Rib and AlphaC [REDACTED] correlate with protection against invasive GBS disease in newborns, makes GBS-NN an ideal candidate for a GSB vaccine with an estimated coverage of 95% of clinical isolates and hence justifies clinical testing of the vaccine.

[REDACTED]

Based on the data derived from the dose ranging studies in mice, it is considered appropriate to commence dosing at 10µg in humans.

The present study will also investigate whether adding the adjuvant Aluminium hydroxide (Alhydrogel®) will improve the immune response, and this will be done in parallel with dosing of GBS-NN.

It is anticipated that dose escalation will occur with a five-fold increment. Dose escalation will only occur after review of safety data up to two weeks after vaccination. At this review a decision will also be made whether a booster dose is required (may be given 28 days after first vaccination).

In Part A, the first cohort will consist of 10 volunteers (8 active, 2 placebo) to receive a dose of 10µg without Alhydrogel®, the second and third cohorts may be dosed in parallel. Cohort 2 will receive a dose of 50µg, without Alhydrogel® and cohort 3 will receive 10µg GBS-NN with Alhydrogel®. Cohorts 4 and 5 may also be dosed in parallel with 250 µg without Alhydrogel® in cohort 4, whilst cohort 5 will receive 50µg with Alhydrogel®. The 6th cohort will receive 250µg GBS-NN with Alhydrogel®.

It is anticipated that the results from Part A will reveal where the optimal dose is likely to lie, and three dose regimens will be selected for evaluation in Part B. In Part B, each cohort will consist of 80 volunteers (60 active, 20 placebo)

It is expected that data accrued from the present study will allow the selection of the most appropriate dose to elicit the best immune response in humans. This dose will then be tested in pregnant women in subsequent studies with an expectation of 95% cover of GBS serotypes compared with 70% achieved with other vaccines.

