15.1.3 Inferential statistics

Adequate statistical tests will be used to carry out comparison between treatment/dose groups performed on primary, secondary or exploratory endpoints, even though it is accepted that the power of these tests for groups in Part A will be low due to small numbers of volunteers.

For categorical endpoints, such as local and systemic reactogenicity, a comparison of events intensity (scores) between vaccine dose groups will be performed with an adequate statistical test dealing with categorical variables (for example: Fisher exact test, Chi square test or generalized estimating equations).

For continuous endpoints, such as immune response induced by different GBS-NN vaccine dosing regimens, appropriate statistical method (for example: ANOVA) will be used to compare pre-vaccination and post-vaccination levels.

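### No listed between-group antibody comparison estimates the Day 1 IgG slope; the SAP should specify a Day 1-adjusted model, mainly for Part B, without pooling residual variance across placebo and vaccine

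*Combined protocol and SAP*

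**What the plan says.** Section 15.4.4 derives two quantities per volunteer from the ELISA: IgG concentration at each sample point, and "Fold increase over pre-immunisation level (Day 1) in antibody concentration at each sample point (ratio". The group endpoints are geometric mean concentration, geometric mean fold increase, seroconversion (fold increase above a threshold) and, at Day 85, proportions above fixed concentrations.

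The same section states that "Statistical tests will be carried out to compare results between treatment groups, depending on studied variable type (see section inferential statistics". For Part B it lists "Placebo group against all other dose groups (regimens to be decided" and "Group A vs Group B; Group A vs Group C; Group B vs GroupC", at Day 29 and Day 84 (read here as the Day 85 visit). Group size comes from section 6.2: "In Part B, each cohort will consist of 80 volunteers (60 active, 20 placebo".

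For method, section 15.1.3 says that an "appropriate statistical method (for example: ANOVA) will be used to compare pre-vaccination and post-vaccination levels". No covariate is named.

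Day 1 IgG is sampled before dosing in both parts (sections 12.2.1 and 12.2.2). In the analyses listed it appears in three places:

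- as the denominator of fold increase, and so behind seroconversion;
- as the pre-vaccination value in the comparison of section 15.1.3;
- in plots of Day 1 against week 12 concentration (section 15.4.4).

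Those plots are the only analysis listed for the secondary objective on pre-existing antibody (section 7.3).

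The protocol does not claim to be complete. The synopsis says that "some (but not all) important features are listed below and presented in the protocol statistical part", and section 15.4.4 adds "These analyses will be fully detailed in the SAP".

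**The concern.** Many women are expected to have natural antibody to these proteins, so Day 1 IgG may predict the later level. The two continuous endpoints treat it in opposite ways: concentration ignores it and fold increase subtracts all of it on the log scale. Which is more precise depends on the pre/post correlation, which the documents do not give.

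Part B is where section 10.1 expects differences in immune response to become measurable. If two regimens differ by chance at Day 1, concentration and fold increase err in opposite directions. Both are Day 85 endpoints of equal standing, and nothing listed says which to believe.

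For the pre-existing-antibody objective, Day 1 and week 12 levels would correlate in placebo recipients too. A plot gives no estimate of whether vaccination changes that relation.

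**Working it through.** **Inputs.** From the protocol: up to 60 vaccine recipients per regimen and 20 placebo per cohort in Part B (180 and 60 over three cohorts); 8 vaccine and 2 placebo per cohort in Part A (48 and 12 over the six defined cohorts). The plan gives no power, SD, effect size, correlation or alpha, so it has no figure to reproduce. Assumed: two-sided 5%, log10 SD 0.4 before and after, true 1.5-fold difference (log10 1.5 = 0.176), pre/post correlation ρ from 0.2 to 0.7, no dropout.

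**Variance relative to concentration** (concentration = 1), n per group:

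- Fold increase: 2(1 − ρ). With k = SD pre / SD post it is 1 + k² − 2ρk, which equals 1 at ρ = k/2. The better fixed slope therefore switches at ρ = 0.5 if k = 1, 0.38 if k = 0.75 and 0.63 if k = 1.25.
- Adjusted model: (1 − ρ²)(1 + 1/(2n − 4)), with one residual degree of freedom less. The second factor is the average cost of chance imbalance.

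**Power at 60 vs 60** (noncentral t):

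| ρ | Variance, fold | Variance, adjusted | Power, concentration | Power, fold | Power, adjusted |
|---|---|---|---|---|---|
| 0.2 | 1.60 | 0.97 | 67% | 47% | 68% |
| 0.3 | 1.40 | 0.92 | 67% | 52% | 70% |
| 0.5 | 1.00 | 0.76 | 67% | 67% | 79% |
| 0.7 | 0.60 | 0.51 | 67% | 87% | 92% |

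Over the same ρ range with SD 0.3: concentration 89%, adjusted 90 to 99%, fold increase 71 to 98%. With SD 0.5: 48%, 49 to 76%, and 33 to 69.5%. At ρ = 0, SD 0.4, the adjusted model loses 0.4 points (66.3% against 66.7%).

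**Chance imbalance at 60 vs 60.** In 1 of 20 pairs the Day 1 gap exceeds 1.96 × 0.4 × √(2/60) = 0.143 log10, or 1.39-fold. At that gap and ρ = 0.3, concentration is off by 0.3 × 0.143 = 0.043 (1.10-fold) one way and fold increase by 0.7 × 0.143 = 0.100 (1.26-fold) the other way.

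**Validity.** In simulations with equal slopes, type I error was about 5% for all three tests at both 60 vs 60 and 8 vs 8.

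**One pooled model over all groups is not safe.** Take slopes of 0.9 in placebo and 0.5 in vaccine, with four groups of 60.

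- Residual variances: 0.16 × (1 − 0.81) = 0.030 and 0.16 × (1 − 0.25) = 0.120.
- Common fitted slope: (0.9 + 3 × 0.5)/4 = 0.6.
- Residual variances around it: 0.0304 + 0.16 × 0.3² = 0.0448 (placebo) and 0.12 + 0.16 × 0.1² = 0.1216 (vaccine).
- Pooled: (0.0448 + 3 × 0.1216)/4 = 0.1024.
- Regimen vs regimen: the effective critical value is 1.96 × √(0.1024/0.1216) = 1.80, so type I error is about 7%.
- Placebo vs regimen: 1.96 × √(2 × 0.1024/(0.0448 + 0.1216)) = 2.17, so about 3%.

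Simulation gives 7.1% and about 3%; the seven-group Part A model gives 6.6% for vaccine vs vaccine. A vaccine-only model or HC3 standard errors bring regimen vs regimen back to 4.7 to 5.1%.

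**Part A.** For a separate 8 vs 8 fit the imbalance cost is 1/12 = 8.3%, so adjustment beats concentration only above ρ = √(1/13) = 0.28. For one fit over the 48 women in six vaccine groups it is 1/(48 − 6 − 2) = 2.5%, with break-even at √(1/41) = 0.16. At 60 vs 60 it is 1/116 = 0.9%, with break-even at √(1/117) = 0.09.

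**Treatment × Day 1 term**, same slopes, separate residual variances. The 95% half-width is 1.96 × √[0.75/(n vaccine − 3) + 0.19/(n placebo − 3)]: ±0.17 at 180 vs 60, ±0.25 at 60 vs 60 (87% power for a slope difference of 0.4), ±0.38 at 48 vs 12 (53%). With equal slopes of 0.3 to 0.5 the intervals are wider: ±0.28 to ±0.26 at 180 vs 60 and ±0.68 to ±0.62 at 48 vs 12.

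**The case against.** The strongest reply is that this is deferred, not omitted. ANOVA is only an example, the comparisons are given in brief, and the SAP may already contain the model. That stands: the point is something not yet specified, and no text rules an adjusted analysis out.

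Second, these are secondary endpoints in a Phase I study whose primary objective is safety, and every figure above rests on an assumed SD, correlation and effect. That also stands, and the gain may be small: 1 to 4 points over concentration if ρ is 0.3 or less, and about 5 points over fold increase at ρ = 0.7. But ρ is unknown, and at 60 vs 60 the adjusted model is at least as good as the better of the two fixed slopes over the range shown.

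Third, a careless adjustment can do harm. The usual single model with one residual variance can push regimen-vs-regimen type I error to about 7%. This is correct, and it determines how the model should be written.

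A reader might infer that the plan ignores baseline altogether. It does not: fold increase and seroconversion both use Day 1, and section 15.1.3 plans a pre/post comparison. Only an estimated slope is missing.

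**Conclusion.** The point holds as a suggestion for the SAP, mainly for Part B. The gain in power at 60 vs 60 ranges from about 1 point over concentration at ρ = 0.2 to about 25 points at ρ = 0.7 (92% against 67%). Against fold increase it runs from about 21 points (68% against 47%) down to about 5. These figures assume equal log10 SDs of 0.4, a 1.5-fold difference and the full planned numbers. The gap on the pre-existing-antibody objective does not depend on ρ: plots alone give no vaccine-against-placebo estimate.

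Two stronger readings are not supported. One is that the listed comparisons are invalid or biased. Under randomisation both hold their type I error, and an imbalance error in a given trial averages to zero. The other is that Part A dose selection is unsound without adjustment. Section 15.1.3 already accepts low power there, and separate 8 vs 8 adjusted fits would lose slightly below ρ of about 0.28. Part A cohorts are also released in sequence (sections 8.1 and 12.5), so adjustment can reduce but not remove differences between them.

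**What to change.** In the SAP:

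1. For Part B at Days 29 and 85, specify a linear model of log10 IgG on group and centred log10 Day 1 IgG. Report adjusted geometric mean ratios with 95% CI beside all the listed endpoints, which stay.
2. Do not share one residual variance across placebo and vaccine. Either fit regimen-vs-regimen contrasts in the vaccine groups only, or use group-specific residual variances or HC3 standard errors for all contrasts. Placebo-vs-regimen contrasts need one of the latter two.
3. For the pre-existing-antibody objective, add a treatment × log10 Day 1 IgG term with placebo as reference and a separate placebo residual variance, mainly in Part B, beside the plots. If slopes differ, read the main ratio as the effect at the mean Day 1 level.
4. Write the below-LLOQ replacement that section 15.2 anticipates and apply it to Day 1 values. With 20 or 40% of Day 1 values set to LLOQ/2 (assumed), adjusted power at ρ = 0.5 is still 78 or 77%.
5. In Part A, treat the model as supportive and fit it over the vaccine groups together. For dose selection the separate unblinded statistician (section 10.4) would need individual Day 1 values; section 15.4.4 describes that blinded report only as endpoints by group.

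The cost is SAP wording, one degree of freedom and about 0.9% in variance at 60 vs 60. No visit, sample or volunteer is added.
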